#### An adverse event can be Anticipated or Unanticipated:

- **Anticipated adverse events** are those that have been previously identified as resulting from the underlying disease, the HCT, or acute GVHD and not related to study drug.
- Unanticipated adverse events are those that vary in nature, intensity or frequency from information in the current anticipated event list, the Investigator's Brochure, the package insert, or when it is not included in the informed consent document as a potential risk. Unanticipated events would also include those that have not been previously described as a result of the underlying disease requiring HCT, the HCT or acute GVHD

## 4.4.2 Classification of Adverse Events by Severity

The severity refers to the intensity of the reported event. The Investigator must categorize the severity of each unanticipated SAE according to the NCI CTCAE version 5.0. CTCAE guidelines can be referenced at the following website: http://ctep.cancer.gov/reporting/ctc.html. For any term that is not specifically listed in the CTCAE scale, intensity will be assigned a grade of one through five using the following CTCAE guidelines:

- **Grade 1**: Mild; asymptomatic or mild symptoms, clinical or diagnostic observations only; intervention not indicated
- **Grade 2**: Moderate; minimal, local or noninvasive intervention indicated; limiting ageappropriate instrumental activities of daily living
- **Grade 3**: Severe or medically significant but not immediately life-threatening; hospitalization or prolongation of hospitalization indicated; disabling; limiting self- care activities of daily living
- Grade 4: Life-threatening consequences; urgent intervention indicated
- **Grade 5**: Death related to AE

## 4.4.3 Classification of Adverse Events by Relationship to Investigational Product

The relationship of each reported event to the study treatment will be assessed by the Investigator; after careful consideration of all relevant factors such as (but not limited to) the underlying study indication, coexisting disease, concomitant medication, relevant history, pattern of the SAE, temporal relationship to any study treatment interventions and dechallenge or rechallenge according to the following guidelines:

- Possibly, Probably, or Definitely Related: there is a reasonable possibility that the study treatment caused the event. A relationship of possibly, probably or definitely related to the investigational product is considered related for the purposes of regulatory authority reporting.
- Unlikely, or Not Related: There is no reasonable possibility that the investigational product caused the event. An unlikely or not related relationship to the investigational product is not considered related for the purposes of regulatory authority reporting. One or more of the following criteria apply:

# 4.4.4 Required Adverse Event Reporting

Any unanticipated SAEs from time of enrollment through the study defined follow up are required to be reported following the BMT CTN Administrative MOP Chapter 6. Additionally, any grade 4 anticipated event not collected on the calendar-driven toxicity or specified event- driven form must **also** be reported through the expedited AE reporting system in Advantage eClinical. Chapter 6 of the BMT CTN MOP defines reporting based on the terms Unexpected and Expected; however, for this study, the reporting will be based on the terms Unanticipated and Anticipated All adverse events, including SAEs, must be reported from the 1st dose of T- Guard through 30 days after the last dose. In addition, any SAEs occurring after that 30-day period, but assessed as related to the investigational product, must be reported. All SAEs are to be followed up until resolved, judged to be no longer clinically significant, or until they become chronic to the extent that they can be fully characterized.

Infections are collected separately in eClinical as this is a study endpoint; however, should an infection meet the SAE criteria the infection must also be reported following the SAE reporting criteria outlined above.

GVHD and underlying disease relapse events are also collected separately in eClinical because they are part of the endpoint analysis. Events of GVHD and underlying disease relapse are not to be reported as AEs/SAEs for this study.

The Sponsor has a list of events classified as Special Situations. These events are 1) medication error, 2) overdose and 3) pregnancy. These events must be reported following the reporting for SAEs.

SAEs that require reporting will be reported through an expedited AE reporting system via an EDC. All SAEs, as well as Special Situations, must be reported within 24 hours of knowledge of the event. Events entered in EDC will be reported using NCI's CTCAE Version 5.0. If there are network outages, a paper copy of the AE form must be completed and emailed to Emmes to initiate Sponsor review. Once the system is available, the event information must be entered into the system.

Anticipated AEs will be reported using NCI's CTCAE Version 5.0 at regular intervals as defined on the Form Submission Schedule, including calendar-driven eCRFs (e.g., Toxicity and GVHD) or event-driven eCRFs (e.g., Relapse/Progression, Infection, Secondary Graft Failure and Death).

The Data and Safety Monitoring Board (DSMB) will receive reports of all unanticipated and unexpected SAEs upon review by the BMT CTN Medical Monitor and the Xenikos Medical Monitor. Summary reports for all reported SAEs will be reviewed by the DSMB on a semi- annual basis.

## 4.4.5 Procedure in Case of Pregnancy

If a female patient becomes pregnant during the study dosing period or within 90 days from the last dose of study drug, the investigator should report the information through an expedited AE reporting system via Advantage eClinical. The expected date of delivery or expected date of the end of the pregnancy, last menstruation, estimated conception date, pregnancy result, neonatal data and other related information will be requested. If a patient becomes pregnant during the study dosing period, the investigational product will be discontinued.

The investigator will follow the medical status of the mother, as well as the fetus, as if the pregnancy is an SAE and will report the outcome. Additional information regarding the outcome of a pregnancy (which is categorized as an SAE) is mentioned below.

- "Spontaneous abortion" includes miscarriage, abortion and missed abortion
- Death of an infant within 30 days after birth should be reported as an SAE regardless of its relationship with the study drug
- If an infant dies more than 30 days after birth, it should be reported if a relationship between the death and intrauterine exposure to the study drug is judged as "possible" by the investigator
- In the case of a delivery of a living newborn, the "normality" of the infant is evaluated at the birth
- Unless a congenital anomaly is identified prior to spontaneous abortion or miscarriage, the embryo or fetus should be assessed for congenital defects by visual examination

Information will be collected at the time of delivery/birth and 180 and 360 days after birth.

# 4.5 INFUSION DELAYS

The visit schedule in eClinical is set up to allow patients a timeline of two days between each infusion visit and a +1-day window for logistics. In the event dosing must be delayed due to occurrence of toxicity, the protocol allows up to 14 days to receive all four infusions. Therefore, instances may occur where a visit falls outside the windows in eClinical that overlap with the visit window for the Day 7 and Day 14 visits. If the infusion visits are delayed, then the assessments for each infusion should still be done and entered into the corresponding visits' forms. Note that the Day 2, 4, and 6 visits directly correlate to Infusion #2, 3, and 4.

For example, if the third infusion (Day 4) is received five days after the second infusion (Day 2), then all the assessments scheduled for the third infusion must be completed. Data for the third infusion would still be entered on the Day 4 forms even though the third infusion occurred on a later day. Similarly, the data for the fourth infusion (Day 6) would be entered on the Day 6 forms although the fourth infusion occurred on a later day.

If an infusion is delayed and occurs on Day 7, then the infusion day assessments must be done while the Day 7 assessments can either be done on the same day or on another day within window, per PI discretion. If all assessments for the infusion (Day 4 or 6) and Day 7 are combined to be completed on the same day, the following should occur:

- Acute GVHD form and Acute GVHD Medications form should be collected and entered in eClinical for the Day 7 visit. A missing form exception should be requested for the Acute GVHD assessment for the infusion visit forms (Day 4 or 6). When requesting a missing form exception, select "Other" as the reason for the missing form exception and specify "Form no longer required, combined with Day [XX] visit".
- The specimen acquisition forms should be completed for both the Day 7 visit and the infusion visit forms (Day 4 or 6) as different samples are required.
  - Day 7: Peripheral blood for ADA, Peripheral blood for GVHD biomarkers REG3α and ST2, and a urine sample for GVHD biomarker 3-IS are to be collected prior to infusion. If the samples can't be drawn pre-infusion, they may be collected the day

after.

- Infusion Visit: CBC with differential, platelet count with differential, and albumin, pharmacokinetics, and Peripheral blood for immunophenotyping are to be collected per protocol.
- The above would still apply if an infusion was delayed to Day 8-10 and the Day 7 visit had not yet been completed.

If an infusion is delayed and occurs on Day 14, then the infusion day assessments must be done while the Day 14 assessments can either be done on the same day or on another day within window, per PI discretion. If all assessments for the infusion (Day 4 or 6) and Day 14 are combined to be completed on the same day, the following should occur:

- Acute GVHD form and Acute GVHD Medications form should be collected and entered in eClinical for the Day 14 visit. A missing form exception should be requested for the Acute GVHD assessment for the infusion visit forms (Day 4 or 6). When requesting a missing form exception, select "Other" as the reason for the missing form exception and specify "Form no longer required, combined with Day [XX] visit".
- The specimen acquisition forms should be completed for both the Day 14 visit and the infusion visit forms (Day 4 or 6) as different samples are required.
  - Day 14: Peripheral blood for ADA, Peripheral blood for GVHD biomarkers REG3α and ST2, and a urine sample for GVHD biomarker 3-IS are to be collected prior to infusion. If the samples can't be drawn pre-infusion, they may be collected the day after.
  - Infusion Visit: CBC with differential, platelet count with differential, and albumin, and pharmacokinetics per protocol
  - Both visits: Peripheral blood for immunophenotyping this should be entered under the infusion visit as it is to be collected pre-infusion and 4 hours post
  - If an infusion is delayed to Day 11-13, the Day 14 visit can be combined as appropriate.

Note:

- There is a 3-day window for the Day 7 and Day 14 visits and visits should be combined when appropriate. However, it's ideal for the assessments to be completed on Day 7 and Day 14.
- Sites are to be mindful of the max blood draw volumes per day for participants and to combine sample collection to avoid unnecessary needle sticks.
- There should be at least 4 but preferably 7 days between the biomarker samples.

# CHAPTER 5

## 5 STATISTICAL CONSIDERATIONS

# 5.1 STUDY DESIGN AND OBJECTIVE

This study is designed as an open-label, single arm, non-comparative, multi-center Phase III study to investigate the efficacy and safety of T-Guard in adult and adolescent patients with SR-aGVHD. A total of 47 patients will be enrolled from approximately 20 transplant centers and treated with T-Guard. The primary objective is to assess the Day 28 CR rate with all patients followed through Day 180 to assess longer term secondary outcomes. As this is a single arm open label study, the analysis will be descriptive, with the target sample size based on ruling out CR rates based on historical data in comparable populations. The target enrollment is 47 patients treated with at least one T-Guard infusion. If any enrolled patients do not initiate T-Guard treatment, additional patients will be enrolled until the goal of 47 treated patients is met. The basis for the sample size, including the underlying meta-analysis, is described in the sequel.

## 5.1.1 Accrual and Study Duration

Accrual is estimated to require 365 days to complete with a total study duration of 545 days.

#### 5.1.2 Randomization and Blinding

No randomization or blinding will occur as this is a single arm open label trial.

## 5.1.3 Analysis Populations

The primary analysis population will consist of all patients who are enrolled and initiate T- Guard treatment. Patients who are enrolled but do not initiate treatment of T-Guard will be described separately.

A PK analysis population will be defined for the assessment of pharmacokinetic and immunogenicity endpoints. This will consist of the set of patients in the primary analysis population from whom samples have been collected and evaluated for these endpoints.

A secondary, supportive analysis of a per protocol (PP) population is planned. The PP population will consist of all enrolled patients who:

- Received four T-Guard infusions
- Met all inclusion and exclusion criteria, with the exceptions of the use of contraceptive and the informed consent (provided a prospective ICF can be obtained)

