# 1.3.3 Justification for the Proposed Dose Regimen for this Phase III Clinical Trial Using T-Guard as First Line SR-GvHD Treatment

The proposed dose for the T-Guard Phase 3 study is  $4 \text{ mg/m}^2$  / dose q 48 hours x 4 doses. This dose is based on the following data:

In the investigator-initiated dose-escalation study (van Oosterhout, van Emst et al. 2000, van Oosterhout, van Emst et al. 2001) it was determined that the second dose level of 4 mg/m^2/dose q 48 hours x 4 doses delivered positive biological and clinical responses, without inducing any severe acute toxicities.

PK analysis showed that the 4 mg/m^2 x 4 doses schedule led to T-Guard *in vivo* serum  $C_{max}$  of around 1.5 µg/ml (~10^-8M). On basis of *in vitro* experiments, the  $C_{max}$  attained results in a 60-80% occupation of the target antigens CD3 and CD7. It has been shown in *in vitro* studies that this concentration is very effective in specifically eliminating antigen-positive target cells by RTA-based immunotoxins (Derocq, Laurent et al. 1987, Preijers, De Witte et al. 1988, Preijers, Tax et al. 1988, Herrera, Farah et al. 2000).

Given the 50% Day 28 CR rate observed in the T-Guard Phase 1/2 study, it could be argued that the clinical benefit may be further optimized by administering a higher T-Guard dose. When judging the response rate, though, consideration is given to the high incidence of serious comorbidities in this severely ill population. Four of the 20 patients of the T-Guard Phase 1/2 study died before Day 28 due to comorbidities; two patients died from sepsis (non- treatment related), one patient died in the treatment week with uncontrolled viral infections, and another patient had vanishing bile duct syndrome with very rare aberrant bile ducts at treatment start suggestive for co-existing liver disease of different etiology. When these four patients are censored, the Day 28 response rate increases to 63% CR (10/16) and 75% ORR (12/16), respectively. In the Phase 1/2 study, the adverse events judged to be potentially treatment-related were clinically manageable and included 7 mild cases (35%) and 1 moderate case (5%) of CLS.

To put the currently applied T-Guard dose in perspective, the Maximum Tolerated Dose as

[figure not shown]

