# 2.5.4 Dose and Administration of T-Guard

T-Guard will be administered at a dose of 4mg/m^2 (actual body weight) over 4 hours every 2 calendar days on Days 0, 2, 4, and 6. Infusions of T-Guard that exceed 4 hours are not considered deviations. Pauses in the infusion due to a patient reaction need to be documented.

The maximum BSA to be used in dose calculation is 2.5 m^2. If the patient's BSA is more than

2.5 m^2, the dose calculation should use 2.5 m^2. The patient's weight on the day of the first dose will determine the dose for the remaining infusions (dose adjustments for changes in weight during the treatment period will not be made).

Premedication with diphenhydramine 50 mg by mouth or 25 mg IV should be administered 30 minutes prior to each dose. For pediatric patients, the diphenhydramine dose should not exceed 1 mg/kg. Premedication with acetaminophen is permitted.

It is recommended that T-Guard be infused via a central catheter using a dedicated line or can be administered via a peripheral line, if needed. If a multi-lumen central venous catheter is used, T-Guard and crystalloid or total parenteral nutrition should be administered through different lumens of the catheter. PK samples should be drawn from the central catheter using a different lumen than the lumen used for infusion.

Before the infusion, connect the syringe with the in-line filter and luer-lock extension tube to a central venous catheter (recommended) or peripheral line. The contents of the syringe will then be administered by means of an automated infusion device, over a period of 4 hours. Once the infusion syringe is empty, the administration tubes will be flushed.

Vital signs (temperature, pulse, respiratory rate, blood pressure), should be checked at the following timepoints with each infusion: just before starting the infusion, 15 minutes after the start of the infusion, 30 minutes after the start of the infusion, then every 30 minutes during the infusion, and at 1-hour post-infusion. Deviation of +/- 5 minutes may occur for all vital sign collection timepoints.

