# 2.5.7 Acute GVHD Progression or Non-response

If additional systemic acute GVHD treatment, other than steroids, is added for lack of response or progression, T-Guard treatment must be discontinued and not re-instituted.

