# 5.4 ANALYSIS OF SECONDARY ENDPOINTS

All secondary endpoints will be reported for the primary and PP analysis groups.

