# 5.4.4 Proportion of Response

The proportion of patients in each aGVHD response category (CR, PR, MR, NR, or progression) will be described at Days 7, 14, 28, and 56 using sample proportions.

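### The per-protocol set requires all four infusions, so deaths and rescues before the fourth dose drop out, which pushes its response rates and survival upward

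*Combined protocol and SAP*

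**What the plan says.** Section 5.1.3 sets the main population broadly: "The primary analysis population will consist of all patients who are enrolled and initiate T- Guard treatment". It then adds a narrower one: "A secondary, supportive analysis of a per protocol (PP) population is planned". Membership of the narrower set has two conditions. The first is that the patient "Received four T-Guard infusions". The second is meeting the eligibility criteria, apart from stated exceptions for contraception and consent. No exception depends on why an infusion was missed.

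The infusions are given "every 2 calendar days on Days 0, 2, 4, and 6" (2.5.4), and the course may run to 14 days from the first dose (2.5.6). If systemic aGVHD treatment other than steroids is added for progression or lack of response, "T-Guard treatment must be discontinued and not re-instituted" (2.5.7).

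Section 5.4 states: "All secondary endpoints will be reported for the primary and PP analysis groups". Those endpoints include OS, timed from the first infusion (5.4.2), and the response categories: "The proportion of patients in each aGVHD response category (CR, PR, MR, NR, or progression) will be described" (5.4.4), with Day 28 among the time points. Section 2.5.9 treats anyone with at least one dose as evaluable for all endpoints.

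**The concern.** A per-protocol set should separate patients handled as the protocol directs from those who were not. This definition does something else. A patient whose T-Guard is stopped because 2.5.7 requires it has been managed according to protocol, yet leaves the PP set. So does a patient who dies before the fourth dose. Selection therefore depends on early outcome.

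For Day 28 CR, both groups are certain failures. Section 3.1 classes patients who receive added systemic therapy as non-responders, and 5.3 counts everyone not in CR at Day 28 as a failure. For OS, NRM and RFS, the early deaths would have been events. Because survival time starts at the first infusion, PP patients cannot die during roughly the first 6 to 14 days. This is the same exclusion of early deaths seen on the time scale, not a second bias.

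In a randomised trial a similar rule would at least act on both arms. Here the only comparison is with a historical rate. What is at stake is the reading of the supportive results: if the primary analysis narrowly fails, a PP result that appears to exclude 30% could be cited alongside it.

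**Working it through.** **1. The plan's own rule.** Section 5.2.1 declares efficacy at 21 or more CRs of 47. An exact binomial calculation of the Simon minimax design reproduces N = 47 with boundaries 6/21 and 20/47. It gives alpha 0.0227, power 0.800, and early-stop probabilities 55.1% at a 30% rate and 3.9% at 50%. Ignoring the non-binding futility rule, P(X ≥ 21 | n = 47, p = 0.30) = 0.0235. So 20/47 = 42.6% fails; its exact one-sided p is 0.046.

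**2. Removing certain failures.** If k patients die or are rescued before dose four, none of them is a CR. The PP rate is x/(47 − k). For x = 20:

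| k removed | PP rate | exact one-sided p against 30% | lower 95% Clopper-Pearson limit |
|---|---|---|---|
| 0 | 20/47 = 42.6% | 0.046 | 28.3% |
| 2 | 20/45 = 44.4% | 0.028 | 29.6% |
| 3 | 20/44 = 45.5% | 0.022 | 30.4% |
| 5 | 20/42 = 47.6% | 0.012 | 32.0% |

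Three removed failures are the fewest for which PP appears to exclude 30% when the primary analysis has failed.

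**3. What k might be.** The documents do not say how many patients will miss a dose, so k is an assumption. In the Phase 1/2 study "one patient died in the treatment week with uncontrolled viral infections" (1.3.3). That is 1 of 20, and 47 × 1/20 = 2.35, about 2 patients, before counting rescues. The number of doses that patient received is not stated.

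**4. Repeated-sampling view.** Let a share d of treated patients be removed, all of them failures. A true rate p in all treated patients becomes p/(1 − d) in PP. At p = 30% this is 31.6%, 33.3% or 35.3% for d = 5%, 10% or 15%. The chance that an exact one-sided 2.5% comparison with 30% would be significant in PP rises from 2.3% at d = 0 to 3.1%, 5.1% or 8.5%. The plan schedules no such test in PP; this only measures how far the set can mislead.

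**5. Survival.** Take the Phase 1/2 Day 180 OS of 60% (1.3.2.3) as the all-treated value, and let d be the share dying before dose four. With no other exclusions, PP survival is 0.60/(1 − d): 63.2% at d = 5% and 66.7% at d = 10%.

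**6. Offsetting exclusions.** A patient who stops for toxicity and is in CR at Day 28 is a success that PP removes. With 3 failures and 2 CRs removed, the rate is 18/42 = 42.9%, almost unchanged. With 2 failures and 2 CRs removed it is 18/43 = 41.9%, below the primary rate.

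**7. An example of direction in the protocol.** Section 1.3.3 sets aside four deaths before Day 28, and CR rises from 10/20 = 50% to 10/16 = 62.5% (printed as 63%). Only one of the four is placed in the treatment week. Removing that one alone gives 10/19 = 52.6%.

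**The case against.** The strongest reply is that little depends on this set. Efficacy is decided only by the Simon boundary in all treated patients. PP is labelled secondary and supportive, 5.1 calls the analysis descriptive, and 5.3 names only the primary population for the Day 28 CR estimate. CR reaches PP through the response categories of 5.4.4, as sample proportions without a test. Both populations are reported, so any gap would be visible. A four-dose set is also objective and prespecified, and it describes patients with full exposure. All of this stands, and it limits the point to the supportive results.

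A reader might also infer more than the documents support:

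- **That PP must always look better than the primary analysis.** Toxicity stops and ineligible patients can be CRs, so the net direction is not guaranteed (step 6).
- **That every excluded patient is both a CR failure and a survival event.** Only deaths are both. Rescue is not an event for OS, NRM or RFS, and a toxicity stop is not automatically either.
- **That progression in the first week removes a patient.** Progression alone does not; 2.5.7 applies when other systemic therapy is added. The window closes at the fourth dose, not at one week, and rescue after that dose leaves the patient in PP.
- **That about 11% will be lost early.** Pooling the two earlier studies gives (2 + 1)/(7 + 20) = 3/27 = 11%. However, the two deaths in the dose-escalation study were in third-line patients, occurred within eight days, and are not stated to have preceded a fourth dose.

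**Conclusion.** The point holds for the supportive PP analysis. Removing deaths and rescues before the fourth infusion pushes PP response rates upward, and removing the deaths does the same for survival. Removing rescued patients raises survival only if, as one would expect, they do worse. The net shift is not fixed, because other exclusions can act either way.

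The size rests on an assumed number of removed failures and no removed CRs. At 2 of 47, the figure closest to the second-line data, a failed 20/47 stays non-significant. At 3 or more it appears to exclude 30%. The primary analysis, the sample size and the 21/47 rule are unaffected. It should be changed because the correction is small and the set as defined does not measure adherence to the protocol.

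**What to change.** In 5.1.3, keep in PP the eligible treated patients whose missed infusions were due to death, added systemic aGVHD therapy, or holding or stopping that the protocol directs. Count them as in the primary analysis. Exclude for missed infusions only when the recorded reason is logistic or administrative. If a four-infusion set is also wanted, label it a completer analysis and start its survival estimates at the fourth infusion.

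The cost is one paragraph plus a rule for classifying reasons for missed doses. Section 2.5.9 already asks for the reason for treatment withdrawal to be documented. Because the trial is open label, the classification rule should be written before the data are reviewed. PP results will be less favourable and closer to the primary analysis. Sample size, decision rule and clinical conduct do not change.
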